completed the 1st cycle, the decision to dose escalate will be deferred until all 6 patients in the group have completed 1 cycle or 28 days of treatment. If no further DLTs are observed in the group then the SRC may dose escalate as appropriate. The same will apply for dose escalation in the subsequent groups. If 2 or more patients in any single group experience DLT the dose will be considered not tolerated. If 2 or more patients experience DLT in the group after the decision has been made to recruit to the next dose level, the dose will still be considered not tolerable, the recruitment to the next dose level stopped and patients within that next group will have their dose reduced to the MTD.

In each group the following therefore applies:

- If no DLT, proceed to next dose group
- If 1 patient experiences a DLT continue until all 6 patients have received 28 days of study treatment before deciding whether to escalate to the next dose level
- If  $\geq 2$  patients out of the group of 6 experience a DLT within the first 28 days of treatment, dose is considered not tolerable.

There will be no intra-patient dose escalation of AZD2281 in this study. If a patient experiences AZD2281 related toxicity, their daily dose of AZD2281 may be reduced or withheld. If the toxicity improves or resolves, the patient may be restarted on AZD2281 at either their initial dose or at a reduced dose. However once a patient has received a reduced dose, re-escalation of AZD2281 to their initial dose level will not be permitted, without prior discussion with the AZ study physician (see Section 6.2.4).

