## 5.5 Discontinuation of patients

### 5.5.1 Criteria for discontinuation

Patients may be discontinued from study treatment and assessments at any time. Specific reasons for discontinuing a patient are given below:

Discontinuation from the study:

- Voluntary withdrawal by the patient who is at any time free to discontinue their participation in the study, without prejudice to further treatment;
- Risk to patients as judged by the Investigator and/or AstraZeneca;
- Severe non-compliance to protocol as judged by the Investigator and/or AstraZeneca;
- Incorrectly enrolled patients, ie, the patient does not meet the required inclusion/exclusion criteria for the study;
- The patient becomes pregnant;
- Patient lost to follow-up.

Discontinuation from study treatment:

- **PK Phase:** Any NCI-CTCAE grade 3 or 4 events that have not reverted to NCI-CTCAE grade 1 or less within 2 weeks (14 days)
- **Continued Supply Phase:** Any NCI-CTCAE grade 3 or 4 events that have not reverted to NCI-CTCAE grade 1 or less within 4 weeks (28 days). (At the Investigator's discretion, following dose interruption, patients may be considered for dose reductions, providing they have not already undergone the maximum number of dose reductions allowed for guidelines see [Table 9](#) and [Table 10](#) for AZD2281. However, if upon re-challenging with AZD2281 at the lowest reduced dose any NCI-CTCAE grade 3 or 4 AEs recur, the patient must be discontinued (refer to Section [6.2.3.2](#)).

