### **6.2.4.2 Continued Supply Phase and Expansion Phase**

Any toxicity observed during the course of the study will be managed by interruption of the dose if deemed appropriate by the Investigator. Repeat dose interruptions are to be allowed as required, for a maximum of 4 weeks (28 days) on each occasion. AZD2281 must be interrupted until the patient recovers completely or the toxicity reverts to NCI-CTCAE version 3.0 grade 1 or less.

Where toxicity recurs following re-challenge with AZD2281, and where further dose interruptions are considered inadequate for management of toxicity, then the patient is to be considered for dose reduction or must permanently discontinue treatment with AZD2281.

Treatment must be interrupted if any NCI-CTCAE grade 3 or 4 AE occurs which the Investigator considers to be related to administration of AZD2281. If this has not resolved to at least NCI-CTCAE grade 1 during the maximum 4 weeks (28 days) dose interruption period, and/or the patient has already undergone the maximum number of dose reductions allowed, the patient must permanently discontinue treatment with AZD2281. If toxicity is appropriately resolved, then the patient should restart treatment with AZD2281 but with a dose reduction according to [Table 9](#) and [Table 10](#). If the event recurs with the same severity, treatment should be interrupted again and, on resolution, a further dose reduction made (see [Table 9](#) and [Table 10](#)). If, on re-starting treatment, the event continues to occur, the patient must permanently discontinue AZD2281.

**Management of new or worsening pulmonary symptoms:** If new or worsening pulmonary symptoms (eg, dyspnoea) or radiological abnormality occurs, an interruption in AZD2281 dosing is recommended and a diagnostic workup (including a high resolution CT scan) should be performed, to exclude pneumonitis. Following investigation, if no evidence of abnormality

is observed on CT imaging and symptoms resolve, then AZD2281 treatment can be restarted, if deemed appropriate by the investigator. If significant pulmonary abnormalities are identified, these need to be discussed with the AstraZeneca Study Delivery Physician.

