**Management of leukopaenia and/or anaemia:** An exception to the management of AZD2281-related toxicity is the occurrence of leukopaenia and/or anaemia. In this case, the AE should be managed as deemed appropriate by the investigator (growth factor, transfusions), without interruption in study drug or change in dose. However, growth factors must be discontinued once the AE has recovered to grade 1 or better. They may be resumed, if necessary, if leukopaenia/anaemia develops again and discontinued once it recovers.

**Management of leukopaenia and/or anaemia (Group 8 and ongoing patients):** An exception to the management of AZD2281-related toxicity is the occurrence of leukopaenia and/or anaemia. In this case, the AE should be managed as deemed appropriate by the investigator (e.g. G-CSF or blood transfusions). However, growth factors must be discontinued once the AE has recovered to grade 1 or better. They may be resumed, if necessary, if leukopaenia/anaemia develops again and discontinued once it recovers. In addition:

- Patients who develop a requirement for repeated blood transfusions within 4-6 weeks should be dose reduced.
- Patients who develop grade 3 anaemia should be dose reduced.

**Management of prolonged haematological toxicities including anaemia, neutropaenia or thrombocytopaenia whilst on study treatment:**

- If any study treatment is interrupted/delayed because of one or more of the following:
- ≥2 week interruption/delay in study treatment due to CTC grade >2 neutropaenia
- ≥2 week interruption/delay in study treatment due to CTC grade >2 thrombocytopaenia
- ≥2 week interruption/delay in study treatment due to CTC grade >2 anaemia and or development of blood transfusion dependence

Weekly blood counts should be performed during the study treatment interruption/delay. If the levels have still not recovered to CTC Grade ≤1 after 4 weeks of dose interruption, the patient should be referred to a haematologist for further investigations. Bone marrow analysis or blood cytogenetic analysis should be considered at this stage according to standard haematological practice. Development of myelodysplastic syndrome should be reported as an SAE and full reports must be provided by the Investigator for documentation on the Patient Safety database.

The dose of AZD2281 must not be adjusted under any other circumstances unless AstraZeneca gives prior agreement. Once the dose of AZD2281 has been reduced under no account should it be re-escalated.

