#### **6.2.4.3 Dose limiting toxicities**

Dose limiting toxicity (DLT) will be defined as any of the following events that is determined to be possibly or probably related to AZD2281 (as determined by the investigator) and occurring during the first cycle of treatment (28 days), irrespective of whether the toxicity resolved:

- ANC < 0.5 x 10^9/L lasting for > 5 days, or ANC < 0.5x10^9/L with neutropenic fever/sepsis.
- Platelet count < 25 x 10^9/L.
- Any other drug-related non-haematological grade 3/4 toxicity, with the exceptions of fatigue, nausea and vomiting, diarrhoea, myalgia or arthralgia unless appropriate prophylactic or therapeutic measures have been administered.
- Unfavourable tolerability profile compared to 400 mg bid capsule profile used in monotherapy in terms of gastrointestinal toxicities and fatigue (grade 3/4)
- Inability to tolerate the cycle of therapy due to toxicity.
- Grade 2 cardiac or neurological toxicity.
- Any toxicity, which in the judgement of the Sponsor and Investigator is viewed as DLT.

- 
- If any haematological or non-haematological toxicities have not resolved ( $\leq$  Grade 1 CTCAE or baseline levels) within 2 weeks, the patient may be considered to have a DLT and may be discontinued from the trial.

In order to define DLT, patients should not be prophylactically prescribed growth factor support, antiemetics, anti-diarrhoeals or antipyretics during cycle 1 of therapy.

If a patient experiences grade 3 or greater nausea and/or vomiting, diarrhoea, medical intervention should occur, including prophylactic administration of these agents for subsequent doses as indicated.

Patients with dose-limiting toxicity after cycle 2 who have documented clinical benefit (stable disease or an objective response) may continue to be treated at a reduced dose level. Any patient in whom a DLT occurs during any cycle will have his or her treatment held until toxicity resolves to baseline or grade 1 or better. Upon resolution, therapy may be re-instituted at the next lower dose level when clinically indicated. Treatment may be delayed up to 2 weeks to allow sufficient time for recovery from toxicities.

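### Return to the initial dose after a reduction is open after discussion in Section 4.1.2.3 but forbidden in Section 6.2.4.2, and the restart dose after related grade 3 or 4 events also conflicts

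*Protocol*

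**What the plan says.** **Re-escalation.** Section 6.2.4.2, on toxicity management in the Continued Supply and Expansion Phases, states: "Once the dose of AZD2281 has been reduced under no account should it be re-escalated". Section 4.1.2.3, on dose escalation within the expansion phase, opens the relevant paragraph with "There will be no intra-patient dose escalation of AZD2281 in this study". It then says that, after a reduction, "re-escalation of AZD2281 to their initial dose level will not be permitted, without prior discussion with the AZ study physician", and refers to Section 6.2.4.

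**Restart dose after toxicity.** Four sections speak to this:

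- Section 4.1.2.3: once drug-related toxicity has improved or resolved, "the patient may be restarted on AZD2281 at either their initial dose or at a reduced dose". No grade is given.
- Section 6.2.4.2: "Treatment must be interrupted if any NCI-CTCAE grade 3 or 4 AE occurs which the Investigator considers to be related to administration of AZD2281". If the event then resolves adequately, "the patient should restart treatment with AZD2281 but with a dose reduction according to" Tables 9 and 10.
- Section 5.5.1, on grade 3 or 4 events in the Continued Supply Phase: "At the Investigator's discretion, following dose interruption, patients may be considered for dose reductions".
- Section 6.2.4.3, after a dose-limiting toxicity (DLT) has resolved: "therapy may be re-instituted at the next lower dose level when clinically indicated".

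**The concern.** An investigator whose patient has been reduced and has recovered needs to know whether the starting dose is available again. One section says that it can be raised with the sponsor's physician; the other says that it is not available at all. An investigator whose patient has recovered from a related grade 3 or 4 event needs to know whether a reduction is required. The answer again depends on the section consulted.

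This matters first for the patient, because one text leaves open a return to the dose at which toxicity occurred and the other closes it. It matters second for the results. Safety and tolerability are the primary objective of the expansion phases. Section 12.4.2.7 summarises safety data descriptively by dose, and Section 12.6.2 summarises laboratory and vital-sign data by dose and formulation received. Section 4.1.4 lets the Safety Review Committee take later-cycle safety data into account when it sets the next dose. If centres in several countries follow different sections, the dose history behind those summaries will vary by centre for reasons unrelated to the drug.

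**Working it through.** No sample size, error rate or event figure enters this point, so there is no arithmetic to reproduce. The check sets the texts side by side.

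1. **Are the texts current?** Yes. All four sections are operative protocol body text, not a change log, and no redaction or removed page explains the difference.

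2. **Do they cover the same patients?** Section 4.1.2.3 concerns the dose-escalation groups. Section 6.2.4.2 is headed for the Continued Supply and Expansion Phases, and its Table 9 gives reductions for Groups 3 to 7. The escalation groups, planned at up to approximately 48 patients, therefore fall under both.

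3. **Re-escalation to the initial dose.** Under Section 4.1.2.3 it is barred by default and open after prior discussion. Under Section 6.2.4.2 it is barred without exception. The conflict is direct.

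4. **Re-escalation to an intermediate level.** The exception in Section 4.1.2.3 names only the initial dose, while the ban in Section 6.2.4.2 covers any increase. For intermediate levels there is no clear conflict.

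5. **Does a nearby clause reconcile them?** The sentence before the ban in Section 6.2.4.2 allows other dose adjustments with AstraZeneca's prior agreement. The ban follows as a separate sentence without that proviso. Discussion with a physician is also not the same condition as agreement.

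6. **Restart dose, toxicity below grade 3.** Section 6.2.4.2 manages toxicity first by interruption and re-challenge, and considers reduction if it recurs. That is compatible with the initial-or-reduced option in Section 4.1.2.3.

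7. **Restart dose, related grade 3 or 4 events.** Section 4.1.2.3 allows the initial dose, Section 6.2.4.2 instructs a reduction, and Section 5.5.1 leaves reduction to discretion. These are an option, an instruction and a discretion for the same situation. Leukopaenia and anaemia stand apart, because Section 6.2.4.2 gives them their own rules.

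8. **Restart dose, DLT.** Section 6.2.4.3 points to the next lower level but in permissive terms. Many DLTs are also related grade 3 or 4 events, so the same patient can meet both the instruction in step 7 and this softer wording. Some DLTs, such as the grade 2 cardiac or neurological ones, fall outside the grade 3 or 4 rule.

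9. **Where the dose enters the analysis.** If summaries follow the dose taken at the time, the section a site follows decides which dose level carries the later data. If they follow the starting dose, it changes the mix of doses within a group. How many patients this affects is not derivable, because the protocol gives no expected rate of grade 3 or 4 events or reductions.

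**The case against.** The strongest reply is that Section 4.1.2.3 is a summary and Section 6.2.4 supplies the detail. On that reading, restarting at the initial or a reduced dose simply describes the two branches of Section 6.2.4.2, and a site that follows the cross-reference arrives at the detailed rule. For toxicity below grade 3 this stands. A reader might infer that the restart dose is contradictory for toxicity of every grade, and the documents do not support that. For related grade 3 or 4 events the reply is weaker: Section 4.1.2.3 carries no grade qualifier, and Section 5.5.1 repeats the discretion. On re-escalation it fails, because a summary cannot contain an exception that the detailed rule excludes.

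A second reply is that the consequences are limited, and this partly stands. Even Section 4.1.2.3 bars re-escalation unless the sponsor's physician has been consulted. Reductions and interruptions are recorded with reasons. Safety comparisons are descriptive. A first-cycle DLT counts whether or not it resolves, so the restart dose cannot undo one already counted.

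A reader might also infer that every patient with a reduction is affected, and that in arms of about 15 each differently handled patient moves a rate by 1/15 = 6.7 percentage points. The documents do not support this. Those arms belong to Groups 6 to 8, whose design sections (4.1.2.4 and 4.1.2.5) contain neither the initial-dose restart option nor the re-escalation exception. The fraction is only the weight of one patient, not an effect. A later re-escalation also does not change whether a reduction took place.

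**Conclusion.** The point holds in a limited form. There is a direct contradiction on return to the initial dose after a reduction, applying at least to Group 3 onwards. There is a narrower conflict on the restart dose, confined to related grade 3 or 4 events outside the separate leukopaenia and anaemia rules, with further differing wording for DLTs. Extending the exception in Section 4.1.2.3 to the whole study would be an inference from its opening sentence, which speaks of the study as a whole but only to rule out intra-patient escalation.

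No magnitude can be given. The conclusion rests on reading the sections as they stand and on the safety summaries depending on dose, as Sections 12.4.2.7 and 12.6.2 say. It should be corrected because it concerns dosing after toxicity, where sites need a single instruction, and because the correction is cheap.

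**What to change.** Reconcile Sections 4.1.2.3, 5.5.1, 6.2.4.2 and 6.2.4.3. One statement should govern re-escalation after a reduction. One should govern the restart dose after a related grade 3 or 4 event or a DLT, and say how it sits with the separate leukopaenia and anaemia rules. The other sections should refer to those statements rather than restate them. Editing only Sections 4.1.2.3 and 6.2.4.2 would leave the discretionary and permissive wording in Sections 5.5.1 and 6.2.4.3 in place. Which rule applies is a clinical decision for the sponsor, and this review takes no position on it. The cost is protocol wording, with no change to sample size, schedule or data collection.

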**Table 9 Dose reductions for AZD2281 (Group 3-7)**

Reduction	Dose Level a	Dose Level a
	Capsule Formulation	Tablet Formulation
Initial Dose Level	400 mg bid	Dose reduce in steps of at least 50mg bid to a minimum daily dose of 100 mg bid after which the patient should be withdrawn from study treatment. A maximum of 3 dose reductions is allowed.
1 st dose reduction due to NCI-CTCAE grade 3 or 4 treatment related SAE/AEs	200 mg bid	
2 nd dose reduction due to NCI-CTCAE grade 3 or 4 treatment related SAE/AEs	100 mg bid	
3 rd Dose Reduction due to NCI-CTCAE grade 3 or 4 treatment-related SAEs/AEs.	No reduction allowed – withdraw patient	

a AZD2281 is not to be decreased below 100 mg bid

**Table 10**                      **Dose reductions for AZD2281 (Group 8)**

Starting Dose	Schedule A: 200mg tds  continuous	Schedule B: 250mg tds  2 weeks on, 1 week off	Schedule C: 400mg bid  1 week on, 1 week off	Schedule D: 400mg od  continuous
Initial dose level	200mg tds	250mg tds	400mg bd	400mg od a
Dose reduction 1	150mg tds	200mg tds	300mg bd	350mg od
Dose reduction 2	100mg tds	150mg tds	250mg bd	300mg od
Dose reduction 3	100mg bd	100mg tds	200mg bd	250mg od

a As an alternative to the first dose reduction the dose for 400mg od schedule the dose may be taken in the evening to manage adverse events if appropriate (e.g. nausea).

At each dose reduction the dosing schedule remains the same (continuous or intermittent at the same schedule as per randomisation), only the dose (mg) is changed.

#### **6.2.4.3 Dose limiting toxicities**

Dose limiting toxicity (DLT) will be defined as any of the following events that is determined to be possibly or probably related to AZD2281 (as determined by the investigator) and occurring during the first cycle of treatment (28 days), irrespective of whether the toxicity resolved:

- ANC < 0.5 x 10^9/L lasting for > 5 days, or ANC < 0.5x10^9/L with neutropenic fever/sepsis.
- Platelet count < 25 x 10^9/L.
- Any other drug-related non-haematological grade 3/4 toxicity, with the exceptions of fatigue, nausea and vomiting, diarrhoea, myalgia or arthralgia unless appropriate prophylactic or therapeutic measures have been administered.
- Unfavourable tolerability profile compared to 400 mg bid capsule profile used in monotherapy in terms of gastrointestinal toxicities and fatigue (grade 3/4)
- Inability to tolerate the cycle of therapy due to toxicity.
- Grade 2 cardiac or neurological toxicity.
- Any toxicity, which in the judgement of the Sponsor and Investigator is viewed as DLT.

- 
- If any haematological or non-haematological toxicities have not resolved ( $\leq$  Grade 1 CTCAE or baseline levels) within 2 weeks, the patient may be considered to have a DLT and may be discontinued from the trial.

In order to define DLT, patients should not be prophylactically prescribed growth factor support, antiemetics, anti-diarrhoeals or antipyretics during cycle 1 of therapy.

If a patient experiences grade 3 or greater nausea and/or vomiting, diarrhoea, medical intervention should occur, including prophylactic administration of these agents for subsequent doses as indicated.

Patients with dose-limiting toxicity after cycle 2 who have documented clinical benefit (stable disease or an objective response) may continue to be treated at a reduced dose level. Any patient in whom a DLT occurs during any cycle will have his or her treatment held until toxicity resolves to baseline or grade 1 or better. Upon resolution, therapy may be re-instituted at the next lower dose level when clinically indicated. Treatment may be delayed up to 2 weeks to allow sufficient time for recovery from toxicities.

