#### **4.1.2.3 Dose escalation within the continued supply expansion phase**

To investigate higher doses of the AZD2281 melt-extrusion (tablet) formulation, up to approximately 48 additional patients will be recruited to the expansion phase in sequential groups:

- A minimum of 6 patients will be recruited to Group 3 which will assess the tolerability and pharmacokinetics of 250 mg bid AZD2281 tablet dose
- If 250 mg bid tablet dose is tolerated, a minimum of 6 patients will be recruited to Group 4 to assess the tolerability and pharmacokinetics of 300 mg bid AZD2281 tablet dose
- If 300 mg bid tablet dose is tolerated, a minimum of 6 patients will be recruited to Group 5 to assess the tolerability and pharmacokinetics of 350 mg bid AZD2281 tablet dose
- If 350 mg bid tablet dose is tolerated, a minimum of 6 patients will be recruited to Group 5.1 to assess the tolerability and pharmacokinetics of 400 mg bid AZD2281 tablet dose
- If 400 mg bid tablet dose is tolerated, dose escalations will continue in a minimum of 6 patients each time to Groups 5.2, 5.3 etc. Dose increases will be at the discretion of the SRC and will continue until the SRC agree that no further doses should be explored.

All dose escalation groups will recruit a minimum of 6 patients. As the dose of AZD2281 tablets at 200 mg bid has already shown to be well-tolerated and the average  $AUC_{0-12}$ , following 250 mg bid tablet dosing, is predicted to be similar to that following 400 mg bid capsule dosing, the study will recruit the 250 mg bid tablet dose group of 6 patients in parallel. This will also be applicable to the subsequent dose escalation groups if the SRC considers this appropriate based on the available safety information.

Once entered into the study, patients will commence 250 mg bid AZD2281 tablet dosing on Day 1 and pharmacokinetic sampling will be performed to obtain PK information after the first dose and at steady state. After the first 3 patients to start treatment have received one cycle of treatment (28 days) the SRC will review all of the available data. If, at this stage, no patient has experienced DLT then 6 new patients will be enrolled into Group 4 at 300 mg bid AZD2281 tablet dose. If one patient in group 3 experiences DLT before all 6 patients have

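### Section 6.2.4.3 caps a toxicity delay at 2 weeks where Sections 6.2.4.2 and 5.5.1 give the same escalation patients 4 weeks, and it uses DLT for cycles outside its own 28-day definition

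*Protocol*

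**What the plan says.** **Time limits.** The closing paragraph of Protocol Section 6.2.4.3 deals with patients who have had a DLT: "Any patient in whom a DLT occurs during any cycle will have his or her treatment held until toxicity resolves", and then "Treatment may be delayed up to 2 weeks to allow sufficient time for recovery from toxicities". The last bullet of the DLT list in that section adds that if a toxicity has not returned to grade 1 or baseline "within 2 weeks, the patient may be considered to have a DLT and may be discontinued from the trial".

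Section 6.2.4.2, on toxicity management in the Continued Supply and Expansion Phases, says "Repeat dose interruptions are to be allowed as required, for a maximum of 4 weeks (28 days) on each occasion". It makes permanent discontinuation mandatory when a related grade 3 or 4 event has not resolved to grade 1 within that period. Section 5.5.1 gives as a reason for stopping treatment in the Continued Supply Phase: "Any NCI-CTCAE grade 3 or 4 events that have not reverted to NCI-CTCAE grade 1 or less within 4 weeks (28 days"). Section 6.2.4.2 also has a pathway for prolonged haematological toxicity. It asks for weekly counts once an interruption has lasted 2 weeks or more, and for referral to a haematologist if there is no recovery after 4 weeks.

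**DLT window.** Section 6.2.4.3 defines a DLT as a related event "occurring during the first cycle of treatment (28 days), irrespective of whether the toxicity resolved". Further down, the section refers to "Patients with dose-limiting toxicity after cycle 2 who have documented clinical benefit" and, as quoted above, to a DLT in any cycle. Section 4.1.2.3 declares a dose not tolerable at 2 or more DLTs. It says so in running text without a time window, and in a summary bullet with a 28-day window.

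**The concern.** Two ceilings are set for the same thing. An investigator holding treatment in an escalation patient cannot tell whether the allowance ends at 2 weeks or at 4. Sites could follow different sections in good faith. Time off drug, restarts and withdrawals would then differ between patients for reasons unrelated to dose, in groups planned at a minimum of 6.

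The DLT wording matters because the DLT count decides whether a dose is tolerable. A term defined for cycle 1 and then applied to later cycles leaves a reader unsure whether later events enter that count. The 2-week non-resolution criterion raises a related question. It needs 14 days to complete, whereas the definition has a 28-day window and the first committee look is timed to it: "After the first 3 patients to start treatment have received one cycle of treatment (28 days) the SRC will review all of the available data". An analysis plan would not normally settle any of this, because these are conduct rules.

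**Working it through.** The protocol gives no error rate, target toxicity rate or power for the escalation rule, so there is no stated figure to reproduce. The check is mainly a comparison of text.

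**1. Do the sections cover the same patients?** Sections 6.2.4.2 and 5.5.1 both refer to Table 9 for dose reductions, and Table 9 is headed for Groups 3 to 7. The escalation groups (3, 4, 5, 5.1 and onward) fall within it. In Sections 5.5.1 and 6.2.4.1, the explicit 2-week limit belongs to the PK Phase. Section 6.2.4.3 claims no precedence over 6.2.4.2.

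**2. The limits side by side**

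| Section | Limit | Force |
|---|---|---|
| 6.2.4.3, delay after a DLT | 2 weeks | ceiling |
| 6.2.4.3, non-resolution bullet | 2 weeks | *may* be a DLT, *may* be withdrawn |
| 6.2.4.2, each interruption | 28 days | ceiling |
| 6.2.4.2, related grade 3/4 unresolved | 28 days | *must* stop |
| 5.5.1, grade 3/4 unresolved | 28 days | listed reason to stop |
| 6.2.4.2, haematological pathway | starts at 2 weeks, referral at 4 | action points |

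If treatment is held from Day h, the ceiling is Day h + 14 under 6.2.4.3 and Day h + 28 under 6.2.4.2. The gap is 28 − 14 = 14 days and the ratio is 28/14 = 2. The haematological pathway begins where the ceiling in 6.2.4.3 ends.

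**3. Which DLTs count?** The definition in 6.2.4.3 says the first 28 days, and so does the summary bullet in 4.1.2.3. The sentences in 6.2.4.3 on later cycles concern holding, reducing and continuing treatment. The running text of 4.1.2.3 states no window.

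**4. The non-resolution criterion.** Assume the 2 weeks run from onset, since the start is not stated. Onset on Day d reaches the mark on Day d + 14, which is within Day 28 only if d ≤ 28 − 14 = 14. Onsets on Days 15 to 28 reach it on Days 29 to 42. The text does not say whether such a case counts.

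**5. Illustration of why one meaning of DLT is needed.** The rates here are assumptions, as the protocol gives none. For 6 patients with per-patient probability p, P(2 or more) = 1 − (1 − p)^6 − 6p(1 − p)^5. If an extra later-cycle risk q also counted, p = 1 − (1 − p1)(1 − q), where p1 is the cycle-1 rate.

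| p1 | 28 days only | q = 5% | q = 10% | q = 20% |
|---|---|---|---|---|
| 5% | 0.033 | 0.109 | 0.212 | 0.442 |
| 10% | 0.114 | 0.212 | 0.320 | 0.536 |
| 20% | 0.345 | 0.442 | 0.536 | 0.699 |

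For p1 = 10% alone: 1 − 0.5314 − 0.3543 = 0.114. With q = 10%, p = 0.19 and the result is 0.320. Only the first column matches the defined window. The others show what a misreading would do and do not measure the size of this finding.

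**The case against.** **On stopping.** An optional withdrawal at 2 weeks and a mandatory stop at 4 can coexist, and 6.2.4.3 could be read as the specific rule for DLT patients with 6.2.4.2 as the general one. The first part stands: a reader might infer that the sections give opposite instructions on who leaves treatment, and they do not. The second part is possible but unstated, and a DLT that is a related grade 3 or 4 event falls under both sections. It does not remove the conflict between the two delay ceilings.

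**On the count.** A reader might infer that what counts against a dose changes with the section followed. The text does not support that. The first-cycle definition is in 6.2.4.3 itself, the summary bullet in 4.1.2.3 repeats 28 days, and no sentence puts a later event into the 2-of-6 rule. What remains is loose use of a defined term.

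**On late onsets.** A reader might also infer that a patient whose 2 weeks are still running at the review is scored as free of DLT. No sentence says so. The criterion is discretionary, and a separate bullet lets the sponsor and investigator call any toxicity a DLT. The committee sees all available data, and Section 4.1.4 lets it use later-cycle information and decline to escalate. Section 4.1.2.3 closes a dose retrospectively at 2 or more DLTs, although a single DLT recognised late is not covered by that safeguard. The listed severe events qualify whether or not they resolve, so Days 15 to 28 are half of the onset days for one residual criterion only. They are not half of DLT detection.

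**Conclusion.** The point holds in a limited form. The 2-week and 4-week ceilings contradict each other for the same escalation patients, with no precedence stated. The conflict bites for toxicities that take between 14 and 28 days to resolve. The protocol gives no basis for saying how many patients that would be.

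The DLT terminology is an inconsistency mainly inside 6.2.4.3. The best reading is that only the first 28 days count in the 2-of-6 rule. Two gaps remain: the running text of 4.1.2.3 has no window, and the status of a non-resolution criterion that completes after Day 28 is not given. The Day 14 cut-off in the working assumes that the 2 weeks run from onset.

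This should be corrected, but it does not show that the escalation rule miscounts DLTs.

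**What to change.** - Reconcile the 2-week and 4-week limits across Sections 6.2.4.3, 6.2.4.2 and 5.5.1. State which limit applies to which patients and events, and which section prevails. Check that the haematological pathway in 6.2.4.2 agrees with the result.
- In 6.2.4.3, use DLT only for events in the defined window and another term for later toxicity. Align the running text of 4.1.2.3 with its summary bullet.
- Reconcile the 2-week non-resolution criterion with the 28-day window and the committee review in 4.1.2.3 and 4.1.4. Say when its clock starts and whether a case that completes after Day 28 is covered.

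The sponsor decides which clinical limits apply; this review proposes none. The cost is protocol wording in these sections, with no change to sample size or data collection.
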